6.3.5 Missing Data

For immunogenicity data, it may be reasonable to consider missing immunogenicity values as missing completely at random (MCAR), i.e., not informative. Therefore, each of immunogenicity analyses will comprise a complete case analysis only, without introducing any bias. Imputation methods will not be used.

6.3.6 Interim Analysis

Not applicable.

6.3.7 Protocol Deviations

6.3.7.1 Definition of Protocol Deviation

Deviations from the protocol will be assessed as ‘minor’ or ‘major’. CSR reportable (“major”) protocol deviations (PDs) are defined in accordance with ICH E3 as important PDs related to study inclusion or exclusion criteria, conduct of the trial, subject management or subject assessment resulting in the potential to jeopardize the safety or rights of the trial subjects or the scientific value of the trial.

All major PDs will be classified into the following categories, but not all deviations listed below will necessarily be declared a major PD:

- Informed Consent
- Inclusion/Exclusion criteria
- Withdrawal Criteria
- Investigational Product (IP) Admin/Study Treat
- Disallowed Medications
- Adverse Event (AE)/ Serious Adverse Event (SAE)

PAREXEL International Statistical Analysis Plan

- Visit Schedule
- Procedure/Tests

Major PDs may result in exclusions of subject from one or more analysis sets according to study-specific PD codes specifications. Major protocol deviations that may lead to exclusion of the subject from PPS1 and/or PPS2 are defined in [Section 6.2.5](#).

The following PD summaries will be provided:

- Number and percentage of subjects with a major protocol deviation by type of deviation and vaccine group

A by-patient listing of protocol deviations will be provided.

6.3.7.2 *Determination of Protocol Deviations*

Prior to unblinding, a PD report will be provided to the Clinical Study Team (CST) consisting of medical, clinical, and operational team members from the Sponsor and CRO for review on an ongoing basis during the study. The PDs review is part of the Data Listing Review process.

After the review, the CST team is responsible for assessing the impact of PDs on the immunogenicity and safety data for study subjects from medical and clinical perspectives. The PDs will be identified and categorized to determine subjects to be excluded from analysis populations according to the PDs specification.

Details of PD review procedure will be provided in the Medical Monitoring Plan and Data Listing Review Manual.

6.3.7.3 *Exclusions of Individual Values for Safety Analysis*

Some local and systemic adverse events (AEs) will be directly measured by the subject and will not be subject to a reconciliation process, even if they are biologically implausible. Therefore, these implausible measurements will be removed from the analysis but included in listings. Implausible measurements are summarized in the [Table 2](#) below:

PAREXEL International
Statistical Analysis Plan

Table 2: Implausible Solicited Adverse Events

Parameter	Implausible measurements
Body temperature	$\leq 33^{\circ}\text{C}$ or $\geq 42^{\circ}\text{C}$
Erythema/Redness	Measurements ≥ 900 mm or Measurements < 0 mm
Induration/Swelling	Measurements ≥ 500 mm or Measurements < 0 mm

6.3.8 Subject Disposition

The following subject data will be presented overall as well as by Sci-B-Vac™ lot, Sci-B-Vac™ treatment group and Engerix-B® treatment group (where possible):

- The number of subjects screened (overall counts only)
- The number of screen failures with a breakdown of reasons for screen failure (overall counts only)
- The number of subject randomized
- The number of subjects dosed.
- The number and percentage of subjects who completed treatment
- The number and percentage of subjects who discontinued from treatment with a breakdown of primary reasons for discontinuation from treatment
- The number and percentage of subjects who completed study
- The number and percentage of subjects who terminated early. The number and percentage of subjects who withdrew early from study with a breakdown of primary reasons for the early withdrawal.

Percentages of subjects will be based on the number of subjects dosed as 100%. All enrolled set will be used for subject disposition.

In addition, by-subject listings will be provided for subjects who discontinued the study early with reason for discontinuation.

PAREXEL International
Statistical Analysis Plan

6.3.9 Demographic Data

All demographic data will be presented for the ITT, FAS, PPS1, PPS2, Safety Set and SSA. All demographic and baseline characteristics will be listed and summarized by Sci-B-Vac™ lot, Sci-B-Vac™ treatment group and Engerix-B® treatment group using appropriate descriptive statistics. Continuous data will be summarized using the number of observations, mean, standard deviation, median, minimum and maximum. Categorical data will be summarized using frequency counts and percentages. No statistical hypothesis testing will be conducted.

6.3.10 Medical History

The frequencies and percentages of subjects with medical history will be presented by MedDRA system organ class and preferred term, by Sci-B-Vac™ lot, Sci-B-Vac™ treatment group and Engerix-B® treatment group. Medical history data will be tabulated for the ITT, FAS, PPS1, PPS2 and Safety Set.

6.3.11 Concomitant Medication

Concomitant medication will be summarized and listed for Safety Set. The frequencies and percentages of subjects reporting concomitant medications will be tabulated by Sci-B-Vac™ lot, Sci-B-Vac™ treatment group and Engerix-B® treatment group. Medications (generic drug name) will be coded using the WHO Drug dictionary.

Prior and concomitant procedures/non-drug therapies will be presented in a listing.

6.3.12 Exposure to the Investigational Medicinal Product

The number of subjects actually receiving the first, second and the third vaccination and the number of subjects received only 1 vaccination, only 2 vaccinations and all three vaccinations will be summarized by Sci-B-Vac™ lot, Sci-B-Vac™ treatment group and Engerix-B® treatment group for safety population.

Vaccine administration information will also be listed.

6.3.13 Immunogenicity

The primary analysis of the immunogenicity data will be based on PPS1 and PPS2. Sensitivity analyses using the same modeling approach will be conducted using the FAS. These analyses will be reported both with and without patients in the FAS who are seropositive at baseline.

Immunogenicity (measurement of anti-HBs titer) data will be listed by subject including actual sampling times relative to dosing. Serum concentrations will be summarized by Sci-B-Vac™ lot, Sci-

PAREXEL International

Statistical Analysis Plan

B-Vac™ treatment group and Engerix-B® treatment group. The following descriptive statistics will be presented for serum concentrations obtained at each time point: n, geometric mean, geometric SD, median, minimum and maximum values.

Individual serum concentration versus actual times will be plotted by Sci-B-Vac™ lot, Sci-B-Vac™ treatment group and Engerix-B® treatment group for anti-HBs antibody in linear and semi-logarithmic scale. The geometric mean serum concentrations with corresponding 95% confidence intervals versus times will also be presented. The bar plot of SPR by treatment on Days 168, 196 and 336 will also be produced based on PPS2. All treatment groups will be overlaid on the same plot.

6.3.13.1 Primary Hypothesis

The lot-to-lot equivalence, in terms of immunogenicity, of three independent consecutive lots of the Sci-B-Vac™ will be demonstrated if the following condition is satisfied:

The upper and lower bound of the two sided 95% CI of the geometric mean concentration (GMC) of anti-HBsAg antibody ratios 4 weeks after the third injection for all three pairwise comparisons (GMC(group A)/GMC(group B), GMC(group A)/GMC(group C), GMC(group B)/GMC(group C)) are within [0.67, 1.5]

The analysis will use a two-sided 5% significance level. PPS1 and PPS2 will be used to test the primary hypothesis.

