CSP	Clinical Study Protocol
CSR	Clinical Study Report
CV	Coefficient of variation
CVID	Common variable immune deficiency
DBP	Diastolic blood pressure
eCRF	Electronic Case Report Form
FDA	Food and Drug Administration
FAS	Full analysis set
GMC	Geometric mean concentration
HBsAg	Hepatitis B surface antigen
HIV	Human immunodeficiency virus
HR	Heart rate
IP	Investigational Product
IWRS	Interactive web response system
LQ	Limit of quantification
MCAR	Missing completely at random
MedDRA	Medical Dictionary for Regulatory Activities
NK	Not known
NOCI	New onset of chronic illness
PD	Protocol deviation
PPS	Per Protocol Set
SAE	Serious adverse event
SAP	Statistical Analysis Plan
SBP	Systolic blood pressure
SD	Standard deviation or single dose

PAREXEL International
Statistical Analysis Plan

Abbreviation / Acronym	Definition / Expansion
SE	Standard error of the mean
SOC	System Organ Class
SPR	Seroprotection rate
SSA	Sub-study Analysis Set
SUSAR	Suspected unexpected serious adverse reactions
TEAE	Treatment-emergent adverse event
TLF	Tables, Listings and Figures
VBI	VBI Vaccines Inc
WHO-DD	World Health Organization - Drug Dictionary

PAREXEL International
Statistical Analysis Plan

STATISTICAL ANALYSIS PLAN

The Statistical Analysis Plan (SAP) details the statistical methodology to be used in analyzing study data and outlines the statistical programming specifications for the Tables, Listings and Figures (TLFs). It describes the variables and populations, anticipated data transformations and manipulations and other details of the analyses not provided in the Clinical Study Protocol (CSP).

The analyses described are based on CSP V4.0, dated 09May2018.

The SAP will be finalized prior to database unblinding and describes the statistical analysis as it is foreseen when the study is being planned. If circumstances should arise during the study rendering this analysis inappropriate, or if improved methods of analysis should arise, updates to the analyses may be made and this SAP will be amended. Any deviations from the SAP after database unblinding, reasons for such deviations and all alternative or additional statistical analyses that may be performed, will be described in the clinical study report (CSR).

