1. STUDY OBJECTIVES

1.1 Primary Objective

To demonstrate the manufacturing equivalence, in terms of immunogenicity, of three independent consecutive lots of the Sci-B-Vac™ 4 weeks after the third vaccination. This objective will be met if the following condition is satisfied:

- The upper and lower bound of the two sided 95% CI of the geometric mean concentration (GMC) of anti-HBs ratios 4 weeks after the third vaccination, for all three pairwise comparisons (GMC of anti-HBs in group A/GMC of anti-HBs in group B, GMC of anti-HBs in group A/GMC of anti-HBs in group C, GMC of anti-HBs in group B/GMC of anti-HBs in group C) are within [0.67, 1.5].

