4. STATISTICAL BASIS FOR SAMPLE SIZE

The sample size for this study is driven by the lot-to-lot consistency requirement. A total of 800 subjects in each of the three Sci-B-Vac™ lots will provide at least 90% power to ensure that the 95% confidence interval for each pairwise difference (GMC of anti-HBs in group A/GMC of anti-HBs in group B, GMC of anti-HBs in group A/ GMC of anti-HBs in group C, GMC of anti-HBs in group B/ GMC of anti-HBs

PAREXEL International Statistical Analysis Plan

in group C) in normalized log₁₀ (GMC) will have a lower bound that is >-0.176 and an upper bound that is <0.176 if the true standard deviation is ≤ 0.9 ; this corresponds to the true GMC ratio falling between $2/3$ and $3/2$. With an active comparator arm of Engerix-B[®] of equal size ($n=800$), the total sample size of the study is 3,200.

If lot-to-lot consistency is demonstrated, all three Sci-B-Vac[™] lots will be pooled together to test that the Seroprotection Rate (SPR) four weeks after completion of the three-dose regimen of Sci-B-Vac[™] is non-inferior to a three-dose regimen of Engerix-B[®]. Assuming 10% of the subjects are non-evaluable (i.e., 2880 are evaluable, with 2160 randomized to Sci-B-Vac[™] and 720 to Engerix-B[®]), a two-sided 5% significance level and a non-inferiority margin of -5% , the non-inferiority test will have $> 90\%$ power. The following table provides the estimated power under different assumptions of the SPR four weeks after completion of the three-dose regimens.

Response in Engerix-B [®] (N=720)	Response in Sci-B-Vac [™] (N=2160)	Power
80%	85%	99%
85%	85%	92%
90%	95%	99%

In October 2018, enrollment was closed early for non-safety-related reasons after 2838 were randomized to the study. With approximately 700 subjects in each of the three Sci-B-Vac[™] lots and 700 subjects in comparator arm of Engerix-B[®], the sample size will provide $> 80\%$ power to evaluate both the primary objective of lot to lot consistency of the three Sci-B-Vac lots, and the secondary objective of non-inferiority of Sci-B-Vac[™] vs Engerix-B[®].

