6.1.1 Derived and Computed Variables

Demographics

Body Mass Index (BMI, kg/m²) will be calculated using the following formula:

$$\text{BMI} = \text{Weight (kg)} / \text{Height}^2 (\text{m}^2)$$

Immunogenicity

Values below the lower limit of quantification (recorded as “< LQ”) will be set to half that limit (LQ/2).

Values above the upper limit of quantification (recorded as “>UQ”) will be set to that upper limit (UQ).

Titer greater or equal to a given threshold is defined as binary variable for non-missing values as:

= 1, if the titer is superior or equal to the given threshold

= 0, otherwise

Seroprotection is defined as binary variable for non-missing values as:

= 1, if anti-HBs levels \geq 10mIU/mL in serum

= 0, otherwise

Seroprotection rate (SPR) is the percentage (%) of subjects achieving seroprotection.

PAREXEL International

Statistical Analysis Plan

An initial result of ≥ 5.0 and < 12.0 mIU/mL (“Indeterminate”) required duplicate retest per Laboratory Procedure Manual. In the statistical analysis, if the anti-HBs serology result is initially indeterminate, then the average of initial and repeat samples will be calculated. Seroprotection will be determined as follows: if the average of initial and repeat samples is ≥ 10 mIU/mL, then it will be considered seroprotected. If it is less than 10 mIU/mL will be considered not seroprotected.

Geometric Mean Concentration

The GMC will be calculated using the following formula:

$$10^{\left\{ \frac{\sum_{i=1}^n \log_{10}(t_i)}{n} \right\}}$$

where t_1, t_2, \dots, t_n are n observed immunogenicity titers/concentrations.

Solicited Adverse Events

Reactions at the site of injection (redness/erythema, pain, tenderness, swelling/edema, pruritus), systemic reactions (nausea/vomiting, diarrhea, headache, fatigue, myalgia) and vital signs abnormalities (fever, tachycardia, bradycardia, hypertension, hypotension, changes in respiratory rate).

Unsolicited Adverse Events

All adverse events will be characterized according to the date of occurrence related to the vaccination phase as follows:

- **Emergence before vaccination phase:** start date before the first date of injection of study vaccine.
- **Emergence during vaccination phase:** start date on or after the first date of injection of study vaccine or, adverse event increase in severity including to “serious” adverse event.

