6.3.13.2 Statistical Methods for Primary Immunogenicity Analyses

Geometric mean concentration (GMC) of anti-HBsAg antibody ratios 4 weeks after the third injection

All statistical analyses will be performed on the logarithmically (base 10) transformed values.

Adjusted estimates of GMCs and their associated 95% CIs will each be determined using an analysis of covariance (ANCOVA) model with a factor for vaccine lot group, and a covariate for the log transformed pre-vaccination (baseline) titer. Data from all centers will be pooled. For each vaccine lot, antibody GMCs, associated standard errors, two-sided 95% CIs and median, minimum, and maximum titer values will be determined and presented by lot group. The median, minimum, and maximum values will be reported on the actual titer values, rather than the log scale. The ratio in GMCs between each vaccine lot group (GMC(group A)/GMC(group B), GMC(group A)/GMC(group C), GMC(group B)/GMC(group C)), and their associated two-sided 95% CIs will also be presented.

PAREXEL International

Statistical Analysis Plan

Sensitivity analyses using the same modeling approach outlined above will be conducted using the FAS. These analyses will be reported both with and without patients in the FAS who are seropositive at baseline.

If this condition is satisfied with either PPS1 or PPS2, then manufacturing equivalence (lot-to-lot consistency) will be demonstrated.

Sample SAS code for assessment of lot-to-lot equivalence:

- Sample SAS code for ANCOVA model:

```
PROC MIXED;  
CLASS treatment;  
MODEL log (var) = treatment log (baseline of var);  
LSMEANS treatment / DIFF CL ALPHA=0.05;  
ODS OUTPUT LSMEANS=ls_means Diffs=diff;  
QUIT;
```

where var represent the anti-HBs titer and treatment represents vaccine lot group.

6.3.13.3 *Secondary Objective Analyses*

If lot-to-lot consistency is demonstrated, then the data from the three lots will be combined to address the secondary immunogenicity non inferiority-hypothesis. It is to demonstrate that the SPR 4 weeks after completion of the three-dose regimen of Sci-B-Vac™ is non-inferior to the SPR 4 weeks after completion of a three-dose regimen of Engerix-B®. Seroprotection is defined as anti-HBs levels ≥ 10 mIU/mL in serum. Seroprotection rate (SPR) is the percentage (%) of subjects achieving seroprotection.

Seroprotection rate (SPR) 4 weeks after the third injection

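### Do the rounded lower limit in [0.67, 1.5] and the log() in the sample code need correcting in the primary lot-consistency analysis?

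*SAP*

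**What the plan says.** - **Success rule.** Sections 1.1 and 6.3.13.1 of the SAP give the same interval with the same fixed numerators (A/B, A/C, B/C): "in group C) are within [0.67, 1.5" and "GMC(group B)/GMC(group C)) are within [0.67, 1.5".
- **Power basis.** Section 4 works on the log10 scale and asks for "a lower bound that is >-0.176 and an upper bound that is <0.176". It adds that "this corresponds to the true GMC ratio falling between" 2/3 and 3/2. The assumed SD is at most 0.9.
- **Log base.** Section 6.3.13.2 says "All statistical analyses will be performed on the logarithmically (base 10) transformed values". Section 6.1.1 introduces its definition with "The GMC will be calculated using the following formula", and that formula is 10 raised to the mean of the log10 titers.
- **Sample code.** The listing in section 6.3.13.2 reads "MODEL log (var) = treatment log (baseline of var" and shows no back-transformation step.
- **Governing protocol.** The SAP introduction states: "The analyses described are based on CSP V4.0". That protocol is not at hand.

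**The concern.** An equivalence interval for a ratio is normally reciprocal, so that A/B and B/A lead to the same answer. Here 1/0.67 is 1.4925, not 1.5. A lower CI limit between 0.6667 and 0.67 would satisfy the margin behind the power calculation and fail the stated rule. In that band the result would also depend on which lot happened to be lettered A. The threshold decides the primary objective and controls whether the lots are pooled for the non-inferiority test, so even a small inconsistency deserves a check.

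The code adds a second doubt. In SAS, log() is the natural logarithm. If natural-log output were back-transformed with powers of 10, every GMC, ratio and CI limit would be wrong. Section 6.3.13.4 points back to the same code for the exploratory GMC analyses.

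**Working it through.** **1. The limits on one scale**

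- log10(0.67) = -0.17393; log10(2/3) = -0.17609; log10(1.5) = +0.17609.
- 10^(-0.176) = 0.66681 and 10^(0.176) = 1.49968, so section 4's 0.176 is itself rounded.
- Gap at the lower end: 0.1760 - 0.1739 = 0.0021 log10. Gap at the upper end: 0.0001.

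The difference is rounding of 2/3, at one end only. It makes the rule stricter.

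**2. Reproducing section 4's power**

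Inputs from section 4: SD 0.9, limits ±0.176, two-sided 95% CI, 800 per lot, at least 90% power for each pairwise difference. Assumption: true lot difference zero, since none is stated.

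Power per pair = Φ(upper/SE - 1.96) - Φ(lower/SE + 1.96), with SE = 0.9 × √(2/n).

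At n = 800, SE = 0.0450 and 0.176/0.0450 - 1.96 = 1.951. Φ(1.951) = 0.9745, so power = 2 × 0.9745 - 1 = 94.9%. The claim of at least 90% per pair reproduces.

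**3. The same calculation under the stated rule**

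| n per lot | ±0.176 | [0.67, 1.5] | Loss (points) |
|---|---|---|---|
| 800 | 94.9% | 94.6% | 0.3 |
| 720 | 92.0% | 91.6% | 0.4 |
| 700 | 91.1% | 90.7% | 0.4 |

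At n = 700, SE = 0.0481 and the CI half-width is 1.96 × 0.0481 = 0.0943. The two margins disagree for a pair only if the estimated log10 ratio lies between -0.1761 + 0.0943 = -0.0818 and -0.1739 + 0.0943 = -0.0796.

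**4. All three pairs together**

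These figures come from simulation: 2,000,000 trials per cell, identical lots, pooled-variance t intervals. The 630 row is an assumption, applying section 4's 10% non-evaluable rate to 700.

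| n per lot | SD | [0.67, 1.5] | 2/3 to 3/2 | Verdicts changed if labels reversed |
|---|---|---|---|---|
| 700 | 0.9 | 78.6% | 79.5% | 1.7% |
| 700 | 0.8 | 91.6% | 92.1% | 1.0% |
| 700 | 0.7 | 98.2% | 98.3% | 0.3% |
| 630 | 0.9 | 70.4% | 71.5% | 2.1% |
| 630 | 0.8 | 86.7% | 87.4% | 1.3% |
| 630 | 0.7 | 96.5% | 96.7% | 0.5% |

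The part due to 0.67 against 2/3 is 0.15 to 1.03 points. The low values at SD 0.9 come from requiring all three pairs at the reduced n, and they are low under either margin.

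If the lots truly differ, the effect can be somewhat larger. With a spread of 0.05 log10 at 800 per lot and SD 0.9 (normal-quantile intervals), joint power is 71.8% under ±0.176. Under the stated rule it is 70.0% or 71.7%, depending on the order of the lots.

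**5. The log base**

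ln y = 2.3026 × log10 y, so on the natural-log scale both the adjusted difference and its SE are multiplied by 2.3026, and e^(2.3026 d) = 10^d. Rescaling the baseline covariate changes only its own slope. One simulated data set (700 per lot) confirms this: SE 0.1100 on ln and 0.0478 on log10 (0.0478 × 2.3026 = 0.1100), with ratio 1.119 and 95% CI 0.902 to 1.388 in both.

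Mixing the bases would turn that CI into 0.788 to 2.127. Such a slip would be conspicuous. A true GMC of 100 mIU/mL would print as 10^(ln 100) = 10^4.605, about 40,300, beside the median, minimum and maximum that section 6.3.13.2 requires on the titer scale.

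**The case for a change.** The strongest case for acting is that each observation is literally true, the threshold is the confirmatory one, and the edit is a few words before unblinding. The lots are exchangeable, so a verdict that can turn on lettering is untidy, and the SAP does not say that 0.67 is rounded. One cell also straddles a stated figure. At 709 per lot (2,838/4, every randomized subject evaluable), SD 0.9 and identical lots, joint power is 80.3% under ±0.176 and 79.6% under [0.67, 1.5], while section 4 claims more than 80%.

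The literal facts stand, but little follows from them.

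- **Straddling 80%.** This needs full evaluability and the SD exactly at its ceiling. The loss is 0.8 point, and section 4's claim is made for about 700 per lot, where joint power at SD 0.9 is below 80% with either margin. Whether the joint requirement was allowed for in that claim is a separate question.
- **Lettering.** The numerators are fixed in advance, so the rule gives one verdict and leaves no choice after the data are seen.
- **Code.** It is headed as a sample and has an English phrase as a function argument. The MODEL statement of PROC MIXED takes variables, so the transformed variable must be created beforehand, and the text says in which base. The 10^ formula in section 6.1.1 takes log10 explicitly. It does not prescribe applying 10^ to natural-log output.
- **Cost.** Using 2/3 loosens a primary limit by 0.0033 in the sponsor's favor after enrollment closed, and may depart from the protocol. Using 1/0.67 tightens the upper limit by 0.0075 and costs another 0.9 point at 700 per lot and SD 0.9 (78.6% to 77.7%).

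**Conclusion.** No change follows. The lower limit is 2/3 rounded to two decimals. It is stated consistently wherever success is defined, it is 0.002 log10 stricter than the powered margin, and it cannot raise the rate of false equivalence claims. Its cost is 0.3 to 0.4 point of power per pair at SD 0.9 and about one point or less for all three pairs, assuming identical lots. It reaches about 1.8 points in the one scenario tried with a 0.05 log10 spread between lots. The per-pair claim of at least 90% at 800 holds with either margin.

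The log() in the listing is a clerical slip. The text fixes base 10, an analyst following it will model log10 values, and consistent use of either base gives the same ratio and CI.

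Following the plan as written leads to a sound primary conclusion. The power figures assume the SD values shown, and the 630 per lot is an assumption. The protocol's own wording of the limit was not available.
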